1.3. Potential Risks and Benefits

As described above, current therapies have limited efficacy in advanced osteosarcoma. SHR-1210 is one humanized PD-1 antibody that is independently researched and developed by Jiangsu Hengrui Medicine Co., Ltd. The preclinical data in animal experiments showed a similar affinity and antitumor effect with nivolumab and pembrolizumab. At the same time, SHR-1210 combined with apatinib has achieved an encouraging preliminary result in treatment of advanced carcinoma. Participation in the phase II study to receive the study drug may bring clinical benefit to patients with advanced osteosarcoma and provide a useful therapeutic option for them.

1.3.1. Known Potential Risks

In the previous clinical studies for multiple solid tumors and hematological tumors, the most common ($\geq 10\%$) adverse reactions induced by SHR-1210 included: reactive cutaneous capillary endothelial proliferation (RCCEP), various rashes, immune endocrine dysfunction such as hyperthyroidism/hypothyroidism, fatigue, elevated transaminase, most of which were Grade 1-2 and could be recovered after symptomatic treatment or dose interruption, had relatively small effect on patient's physiological function and quality of life, and did not hinder continuation of the study treatment. RCCEP is a unique skin reaction of SHR-1210. Although with a relatively high incidence in the SHR-1210 monotherapy, RCCEP was relatively mild in severity and clinically tolerable, and could be recovered after discontinuation of the drug. Moreover, in the treatment of SHR-1210 combined with apatinib, the incidence of RCCEP was significantly reduced, which may be related to the anti-angiogenic effect of apatinib. The most common serious adverse reactions of SHR-1210 include pneumonitis, abnormal liver function, lung infection and thrombocytopenia. Various immune-related adverse reactions are potential risks of SHR-1210, which are class effects of PD-1 antibody preparations and include pneumonitis, hepatitis, thyroiditis, myocarditis, enteritis, etc. Symptomatic treatment will be given in accordance with EMSO/NCCN guideline on management of immunotoxicity and can ensure the safety of patients during the trial. Please refer to the investigator's brochure for more details on adverse drug reactions associated with SHR-1210.

Apatinib mesylate tablets were approved by the Chinese drug regulatory authorities for the treatment of advanced gastric cancer in October 2014. The recommended initial dose is 850 mg, orally, once daily. The most common ($\geq 10\%$) adverse reactions of apatinib (850 mg QD) are hand and foot skin reactions, hypertension, elevated transaminases, elevated bilirubin, elevated alkaline phosphatase, elevated γ -glutamyl transferase, proteinuria, diarrhea, leukopenia, thrombocytopenia, anemia, fatigue, etc., most of which are mild to moderate reactions and can be recovered or improved after the drug is temporarily discontinued and treatment is given. In addition, the use of apatinib requires special attention to events that have a low incidence but may cause serious consequences or even deaths, including various types of bleeding and thrombotic events, cardiotoxicity (QT interval prolongation, arrhythmia) and liver toxicity. Please refer to the investigator's brochure for more details on adverse drug reactions associated with apatinib mesylate. Currently, the known safety information on apatinib mesylate mainly comes from the experience of dose regimen of 850 mg QD, and the experience of 250 mg QD is relatively limited.

Although the mechanism of action for SHR-1210 and apatinib is completely different, their pharmacological effects may extensively affect multiple organ systems of the body. Based on the preliminary safety data, and given that there could be overlapped adverse reactions associated with both drugs during the treatment of SHR-1210 in combination with apatinib 500 mg QD, overlapped adverse reactions that require the investigator's special attention include but not limited to: various rashes, hematological toxicity, abnormal liver function, diarrhea, anorexia, proteinuria and fatigue.

1.3.2. Known Possible Benefits

The osteosarcoma patients enrolled in this study may achieve partial or even complete response, and some patients may obtain sustained stable disease. The above trial data will provide a strong guidance for the clinical practice for osteosarcoma treatment and allow more patients to access and benefit from new therapeutic methods.

2. STUDY OBJECTIVES AND ENDPOINTS

| Primary Study Objective | Primary Study Endpoints |
|---|---|
| 
 To observe the Clinical Benefit Rate (CBR) and Progression Free survival Rate (PFR) of mesylate apatinib combined with SHR-1210 as second/third-line therapy for patients with advanced osteosarcoma who have progressed upon chemotherapy. | 
 Clinical Benefit Rate (CBR); Progression Free survival Rate (PFR) of 6 month evaluated by the blinded independent review committee (BIRC) based on RECIST v1.1. |
| Secondary Study Objectives | Secondary Study Endpoints |
| 
 To compare the efficacy of mesylate apatinib combined with SHR-1210 in patients with advanced osteosarcoma, who have progressed upon chemotherapy, through evaluations of overall survival (OS), objective response rate (ORR), disease control rate (DCR), and duration of response (DoR); | 
 Objective response rate (ORR), disease control rate (DCR), and duration of response (DoR) evaluated by BIRC based on RECIST v1.1; PFS, ORR, DCR and DoR evaluated by investigator based on RECIST v1.1; PFS, ORR, DCR and DoR evaluated by BIRC based on the immune-related response criteria (irRC). |
| 
 To evaluate the safety of mesylate apatinib combined with SHR-1210 in patients with advanced osteosarcoma, who have progressed upon chemotherapy; | 
 Incidence and severity of adverse event (AE) and serious adverse event (SAE) judged in accordance with NCI-CTCAE v4.03; vital signs, ECG and abnormal laboratory examinations; |
| Exploratory Study Objectives | Exploratory Study Endpoints: |
| 
 To evaluate the quality of life (QoL), including general health status (GHS), physical functioning and role functioning, of patients with advanced osteosarcoma who receive mesylate apatinib | 
 Time to deterioration (TTD): defined as time from randomization to first deterioration, as determined by following subscales of European Organization for Research and Treatment of Cancer (EORTC) Quality-of-Life Questionnaire-Core 30 (QLQ-C30) (ie, a decreased in score by ≥ 10 |

| | |
|---|---|
| 
combined with SHR-1210;
 | 
from baseline maintained for two consecutive time points, or one time-point followed by death [from any cause] within 3 weeks):
 
 - Global health status - Physical Functioning - Role Functioning |
| 
 • To explore the correlation between biomarkers and the efficacy of combined therapeutic regimen; | 
 • Average score and its change in the score from baseline in all the subscales of EORTC QLQ-C30 (by cycle); • The correlation of the expression level of PD-L1 and proportion of strong expression of PD-L1 in tumor tissue with the efficacy of mesylate apatinib combined with SHR-1210 (including but not limited to PFS, ORR, OS); |

3. STUDY DESIGN

3.1. Overall Design

This is a Single-arm, Open label, Prospective, Single-center phase II trial to evaluate the efficacy and safety of PD-1 antibody SHR-1210 plus apatinib mesylate as seconde/third-line therapy in patients with advanced osteosarcoma.

The study will be conducted in subjects with incurable, locally advanced or metastatic osteosarcoma who had progressed upon first-line/second-line chemotherapy including high-dose methotrexate, doxorubicin, cisplatin with or without ifosfamide. Primary efficacy endpoints include both CBR and PFS evaluated by the BIRC based on RECIST v1.1, and approximately 43 subjects will be enrolled. Eligible subjects will receive SHR-1210 combined with apatinib mesylate (experimental arm).

Subjects will receive study treatment after being informed of all pertinent aspects of the study, signing the informed consent form and passing the screening for eligibility. Experimental arm: SHR-1210, 200 mg, via intravenous infusion, once every two weeks (Q2W) + apatinib mesylate 500 mg, p.o., once per day (QD), continuously, 4 weeks (28 days) per cycle of therapy, until meeting the criteria for study treatment termination specified in the protocol. Subjects will continue to receive safety and survival follow-up after end of treatment. Subjects who discontinue treatment for reasons other than progression of disease will continue to receive regular radiological evaluation follow-up after end of treatment.

The subject will continue to receive study treatment until intolerable toxicity occurs, or until lack of clinical benefits as determined by investigator after comprehensive evaluation of radiological and laboratory examination data as well as the subject's

clinical condition (e.g., tumor symptomatic exacerbation), or until the subject voluntarily withdraws from study treatment, whichever comes first.

Following disease progression in accordance with RECIST v1.1 (evaluated by investigator), subjects may continue treatment with SHR-1210 monotherapy or in combination with apatinib, if they can still clinically benefit from and tolerate study treatment as determined by investigator (see Section 6.6 for treatment criteria after disease progression).

Subjects will have safety visits on D1 and D15 of each cycle of therapy within the first 3 cycles for both arms. Beginning from the 4th cycle, subjects will have safety visits on D1 and D15 of each cycle in the experimental arm; subjects in the control arm will only have safety visits on D1 of each cycle. Radiological examination will be performed once every 8 weeks to evaluate efficacy for the first 33 cycles, and once every 12 weeks thereafter, until progression of disease is determined (non-pseudoprogression), start of a new anti-tumor therapy, withdrawal of informed consent, death, or termination of the study by the sponsor, whichever comes first. The study design is shown in Figure 4.

[figure not shown]

Figure 4. Study Design Chart

4. SELECTION AND WITHDRAWAL OF SUBJECTS

Subjects can be allowed to participate in this study only when they meet the following criteria. All the medical and non-medical conditions of each subject are considered as to whether they meet the study criteria.

Investigators should review, confirm and record whether the subject is suitable for participation in this study prior to enrollment.

4.1. Inclusion Criteria

Subjects can be enrolled in this study only when they meet all the inclusion criteria:

1. Provided informed consent and sign the informed consent form;

2. ≥ 11 years old, male and female;
3. Histopathologically or cytologically confirmed Advanced Osteosarcoma; (Local tumors and solitary pulmonary lesions must be confirmed by pathological diagnosis. Multiple pulmonary metastases need no pathological examination.)
4. Failed to receive chemotherapy for osteosarcoma (including high-dose methotrexate, anthracyclines, cisplatin and ifosfamide) are defined as those who progress within 6 months after adjuvant chemotherapy and chemotherapy for advanced osteosarcoma, and those who progress over 6 months require the consent of the subject or his legal representative.;
5. Have at least one measurable lesion (in accordance with RECIST v1.1, major diameter ≥ 10 mm of the measurable lesion in spiral CT scan or short diameter of swollen lymph node ≥ 15 mm; the lesion with previous local therapy can be used as target lesion after the progression is confirmed in accordance with RECIST v1.1);
6. For subjects with progression after local regional therapy, the local regional therapy (including but not limited to surgery, radiotherapy, hepatic artery embolization, TACE, hepatic arterial infusion, radiofrequency ablation, cryoablation or percutaneous ethanol injection) must have been completed at least 4 weeks prior to baseline radiological scanning, and any toxicity (except alopecia) induced by local regional therapy must have resolved to \leq Grade 1 in accordance with national cancer institute – common terminology criteria for adverse event version 4.03 (NCI-CTCAE v4.03);
7. ECOG-PS score 0-1(see APPENDIX 2);
8. With a life expectancy of ≥ 12 weeks;
9. The body surface area is over 1.2m^2 ;
10. Have the required screening laboratory values including the following parameters (within 7 days prior to the start of study treatment):
11. Hematology: (except for hemoglobin, no blood transfusion or use of granulocyte colony-stimulating factor [G-CSF] or use of drugs for correction within 14 days prior to screening);
 - Absolute neutrophil count $\geq 0.75 \times 10^9/\text{L}$;
 - Platelet count $\geq 75 \times 10^9/\text{L}$;
 - Hemoglobin ≥ 80 g/L;
 - Blood biochemistry: (no infusion of albumin within 14 days):
 - Serum albumin ≥ 25 g/L;
 - Serum total bilirubin $\leq 1 \times$ upper limit of normal (ULN);
 - Alanine aminotransferase (ALT), aspartate aminotransferase (AST) and alkaline phosphatase (AKP) $\leq 2.5 \times$ ULN;
12. Serum creatinine (Cr) ≤ 1.5 ULN or Cr clearance >50 mL/min (Cockcroft-

Gault formula as below)

Man: Cr clearance = $((140 - \text{age}) \times \text{weight}) / (72 \times \text{serum Cr})$

Woman: Cr clearance = $((140 - \text{age}) \times \text{weight}) / (72 \times \text{serum Cr}) \times 0.85$

Weight unit: kg; serum Cr unit: mg/mL;

13. Women of childbearing potential: must agree on abstinence (avoid heterosexual intercourse) or use of contraception methods with annual contraceptive failure rate of < 1% following the signature of informed consent form until at least 120 days after the last dose of study drug. The serum human chorionic gonadotropin (HCG) test must be negative within 7 days prior to enrollment in the study; and the subjects must not be in lactating period.
14. If the female subject has menses, has not reached postmenopausal state (absence of menses for \geq consecutive 12 months, with no other reason found except menopause) and has not received sterilization operation (e.g., hysterectomy, bilateral tubal ligation or bilateral ovariectomy), she would be considered to have childbearing potential.

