- e. does not need to recalculate BSA every cycle unless the research center guidelines require or subjects to gain or lose more than 10% of their original weight. For obese subjects (BMI > 30), BSA should be calculated using ideal body weight throughout the study period.
- f. To record adverse events within 4 weeks after the last administration of the drug. Drug-related grade 3 or 4 toxicity was monitored until it was reduced to grade 2 or below, or at least 24 weeks after the last drug administration, whichever was earlier. Liver or cardiac toxicity of grade 2 to 4 was monitored until it dropped to grade 1 or below, or at least 24 weeks after the last administration of the drug, whichever was earlier.
- g. Records only the date when new cancer treatments are initiated.
- h. Laboratory results must be obtained within 48 hours before administration.
- i. applies only to women of childbearing age who have sex.
- j. Survival status should be followed up at least every 12 weeks within 2 years after the last administration of the drug, and then every 24 weeks until the end of the clinical study.
- k. The formula of creatinine clearance was: $\text{Cr} = (140 - \text{age}) * \text{body weight}(\text{kg}) / [72 * \text{Scr}(\text{mg/dl})]$ or $\text{Cr} = [(140 - \text{age}) * \text{body weight}(\text{kg})] / [0.818 * \text{Scr}(\text{umol/L})]$. Women were calculated by the result *0.85

ABBREVIATIONS

| Abbreviations | Definition |
|------------------|---|
| AE | adverse event |
| ADA | antidrug antibody |
| ALP | alkaline phosphatase |
| ALT | alanine aminotransferase |
| AST | aspartate aminotransferase |
| AUC | area under the concentration time curve |
| BID | twice daily |
| BOR | best overall response |
| BUN | blood urea nitrogen |
| CK | creatinine kinase |
| C _{max} | maximum concentration |
| Cr | creatinine |
| CT | computed tomography |
| CTLA4 | cytotoxic T lymphocyte antigen 4 |
| D | Day |
| DCR | disease control rate |
| DNA | deoxyribonucleic acid |
| DoR | duration of response |
| eCRF | electronic case report form |
| ECOG-PS | Eastern Cooperative Oncology Group- Performance Status |
| EDC | electronic data capture |
| EORTC | European Organization for the Research and Treatment of Cancer |
| FAS | full analysis set |
| G-CSF | granulocyte colony-stimulating factor |
| GCP | Good Clinical Practice |
| GGT | γ-glutamyl transferase |
| GHS | general health status |
| h | hour |
| HBsAg | Hepatitis B surface antigen |

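### The eligibility creatinine-clearance formula gives serum creatinine in mg/mL, which inflates clearance 100-fold and leaves the >50 mL/min limit practically impossible to fail

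*Protocol*

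**What the plan says.** The renal inclusion criterion appears twice: in the synopsis (Inclusion Criteria, item 10) and in Protocol Section 4.1 (item 12). A patient qualifies with serum creatinine of at most 1.5 × ULN, or with a clearance above 50 mL/min by Cockcroft-Gault. In both places the formula for men is (140 − age) × weight divided by (72 × serum creatinine), with a factor of 0.85 for women. In both places the units are given as "Weight unit: kg; serum Cr unit: mg/mL".

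Footnote k of the Schedule of Activities, which opens "The formula of creatinine clearance was", gives the same expression with the same constant 72 but with creatinine in mg/dl. It adds a second form with constant 0.818 for creatinine in µmol/L, and the same factor of 0.85 for women.

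**The concern.** The protocol attaches two different units to one constant, and they differ 100-fold, so at most one can be right. If mg/mL is the wrong one, a clearance calculated as the eligibility lists instruct is 100 times too large.

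The two arms of the criterion are joined by an or. A clearance arm that always passes therefore makes the creatinine arm irrelevant as well, and the only numeric renal limit for entry stops excluding anyone. The exclusion list in Section 4.2 contains no renal-function threshold that would take its place. The population makes the screen relevant: Section 4.1 requires prior chemotherapy that includes high-dose methotrexate, cisplatin and ifosfamide, and Section 1.3.1 lists proteinuria among the overlapping reactions of the two study drugs.

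**Working it through.** **Inputs from the protocol.** Constant 72, factor 0.85 for women, limit >50 mL/min, unit mg/mL (synopsis and Section 4.1). Constants 72 with mg/dl and 0.818 with µmol/L (footnote k). Lower age limit: "≥ 11 years old, male and female" (Section 4.1). Age 24.5 is the median of the retrospective apatinib sarcoma series in Section 1.2.2.2, used here only as a plausible age.

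**Assumptions.** All body weights, and all other ages above the lower limit. Molar mass of creatinine about 113.12 g/mol, so 1 mg/dL is about 88.4 µmol/L.

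**Step 1: which unit belongs with 72.** Footnote k's two forms must give the same clearance, so its constants imply 72 / 0.818 = 88.0 µmol/L per unit of the first form. That matches 1 mg/dL (88.4). In the other direction, 72 / 88.4 = 0.814 against the stated 0.818, a difference of about 0.4%, so footnote k is reproduced. If 72 belonged with mg/mL, the µmol/L constant would be 72 / 8,840 = 0.0081, which is 100 times smaller than the one printed.

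**Step 2: size of the error.** 1 mg/dL = 0.01 mg/mL. Creatinine is in the denominator, so using mg/mL multiplies clearance by exactly 100. The printed limit of 50 is then a limit of 0.5 mL/min on the mg/dL scale.

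**Step 3: example.** Man, age 24.5, 55 kg. Numerator: (140 − 24.5) × 55 = 6,352.5.

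- Creatinine 2.0 mg/dL: 6,352.5 / (72 × 2.0) = 44.1 mL/min. As printed: 6,352.5 / (72 × 0.02) = 4,411 mL/min.
- Creatinine 8.0 mg/dL: 6,352.5 / (72 × 8.0) = 11.0 mL/min. As printed: 6,352.5 / (72 × 0.08) = 1,103 mL/min.
- Creatinine at which clearance falls to 50: 6,352.5 / (72 × 50) = 1.76. This is 1.76 mg/dL on footnote k's scale, but 1.76 mg/mL = 176 mg/dL as printed.

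**Step 4: range.** The creatinine at which the clearance arm starts to fail is (140 − age) × weight × sex factor / (72 × 50).

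| Assumed patient | Fails from, unit mg/dL | Fails from, as printed (in mg/dL) |
|---|---|---|
| Woman, 80 y, 40 kg | 0.57 | 56.7 |
| Woman, 60 y, 50 kg | 0.94 | 94.4 |
| Girl, 11 y, 35 kg | 1.07 | 106.6 |
| Boy, 11 y, 35 kg | 1.25 | 125.4 |
| Woman, 25 y, 55 kg | 1.49 | 149.3 |
| Man, 24.5 y, 55 kg | 1.76 | 176 |
| Man, 20 y, 60 kg | 2.0 | 200 |

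**Step 5: the other arm.** A patient is excluded only if creatinine also exceeds 1.5 × ULN, and the protocol gives no ULN. With the correct unit, the man in Step 3 at 2.0 mg/dL fails the whole criterion if the ULN is below 2.0 / 1.5 = 1.33 mg/dL. At 8.0 mg/dL he fails it if the ULN is below 8.0 / 1.5 = 5.33 mg/dL. As printed he passes in both cases, whatever the ULN.

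**The case against.** The best reply is that this is a slip in a unit label with little practical reach. The formula is named, so anyone who knows it will enter mg/dL and get the intended value. The inflated figure appears only if someone converts a result to mg/mL first, and a clearance in the thousands would be noticed at once. The trial has one centre, so different readings between sites are not an issue. Nothing says that the eCRF computes clearance: Sections 11.1.3 and 11.2.1 describe logic checks and a database built to the protocol only in general terms. Other safeguards remain. Exclusion 27 covers serious laboratory abnormalities, Section 4 requires all medical conditions to be considered, and Section 6.1 requires creatinine, urea and urinalysis within 7 days before the first dose. Finally, in the schedule as it can be read here, the marker for footnote k does not sit on a renal row, so the footnote is not shown to govern eligibility; the table may have been damaged in extraction.

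Most of this stands as a limit on the consequence. Harm depends on literal application, and failing the printed limit is practically impossible rather than mathematically so. None of it makes the printed unit right. The remaining safeguards are matters of judgement and set no numeric renal limit. The contradiction does not depend on which schedule row footnote k belongs to, because the constant and the units disagree wherever the footnote applies. The same wrong unit in both eligibility lists also means that a comparison of synopsis and body would not reveal it.

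**Conclusion.** The concern holds. Both eligibility lists give a creatinine unit that does not fit their own constant and that contradicts footnote k. The error is exactly 100-fold and needs no assumption beyond the conversion between mL and dL. That the limit then excludes no realistic patient rests on assumed ages and weights, but over the range shown the printed threshold lies at roughly 57 to 200 mg/dL, so the conclusion is not sensitive to them. Through the or, the whole renal criterion becomes non-restrictive when read literally.

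The primary endpoint, sample size and analysis are unaffected. The correction should still be made, because this is an operative enrolment threshold that works only if the reader silently overrides the text. No view is taken on the value of 50 mL/min or on the 1.5 × ULN limit.

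**What to change.** Replace mg/mL with mg/dL in the synopsis inclusion criteria (item 10) and in Section 4.1 (item 12), so that both agree with footnote k. If the laboratory reports in µmol/L, refer from the criterion to footnote k's second form. Confirm that any eCRF edit check or screening worksheet built from Section 4.1 uses the corrected unit. If enrolment has begun, recalculate clearance for enrolled patients from the recorded creatinine, age, weight and sex. The cost is one unit in two places and a short check of the data-entry rules; no limit or analysis changes.
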